12.0 APPENDICES

APPENDIX I: Definitions for severe or invasive infections in ZIPS study

Infection	Definition
Abscess	Opaque, fluid-filled/fluctuant collection on skin (with purulent discharge if drained)
Bacteremia	Children with a positive blood culture with a true pathogen (e.g., S. aureus , S. pneumoniae , Salmonella , other Gram negative infections)
Cellulitis	Area of reddened, warm skin in a child with a history of fever or measured axillary temperature of $\geq 37.5^{\circ}\text{C}$
Diarrhea	More than 3 loose stools in a 24-hour period
Dysentery	Fever with bloody stools
Malaria	Measured fever (axillary temperature $\geq 37.5^{\circ}\text{C}$) or fever by history and Plasmodium species infection on blood smear
Meningitis/Encephalitis	Fever with 1) nuchal rigidity or altered mental status and 2) CSF with >5 WBC or with positive CSF culture for meningitis-associated organisms (e.g., S. pneumoniae , N. meningitidis , H. influenzae)
Osteomyelitis	Fever with bone pain, redness of skin over bone and x-ray findings consistent with osteomyelitis
Pharyngitis/Tonsillitis	Inflamed, erythematous pharynx and/or tonsils, with pharyngeal or tonsillar exudate
Pneumonia/Acute Chest Syndrome (ACS)	Pneumonia: history of fever or measured axillary temperature $\geq 37.5^{\circ}\text{C}$, with age-specific tachypnea, cough, and an infiltrate and/or effusion on chest x-ray consistent with pneumonia* Acute chest syndrome: signs of pneumonia above plus chest pain and/or tenderness
Sepsis	Meets modified criteria for SIRS/sepsis in International pediatric sepsis consensus guidelines (2 or more of the following criteria, one of which must be abnormal temperature: $T \geq 38.5^{\circ}\text{C}$, age-specific tachycardia, age-specific tachypnea, age-specific leukopenia). Modified to remove leukocytosis because, per NOHARM study data, $>80\%$ of children with SCA at Mulago Hospital will have age-specific leukocytosis at baseline, which is an IPSC criterion for SIRS/sepsis. Since SIRS in a child with SCA is always suspected to be due to infection, we will use the term sepsis.
Sinusitis (acute)	Congestion, nasal discharge or cough for more than 10 days without improvement; or symptoms of congestion with purulent nasal discharge for more than 3 days
Urinary tract infection	Symptoms (fever with urinary frequency, burning or new incontinence after prior toilet training) plus urinalysis positive for LE or nitrite OR clean catch urine culture with $>100,000$ colonies of a single pathogen

* Any child with a standard clinical diagnosis of pneumonia (clinical signs above) will be treated for pneumonia regardless of CXR findings, as this is Mulago Hospital Sickle Cell Clinic protocol. Chest x-rays will be read by on call radiologist for acute clinical care, and also saved for reading by second radiologist. Specific criteria will be assessed by both radiologists, and only children who meet criteria from the WHO Radiology Working Group for pneumonia will be given a final diagnosis of pneumonia (Cherian T et al, Bulletin of WHO, 2005;83:353-359). Children who do not meet radiographic criteria will be given a final diagnosis of “respiratory infection” and not included in primary category of “severe or invasive infections” that constitutes the primary study endpoint. They will be considered for the secondary endpoint of “all clinical infections”.

APPENDIX II. Common Terminology Criteria for Adverse Events (CTCAE) Version 4.0 and Exceptions to CTCAE

Table 1. Sickle Cell Disease Symptoms and Associated Conditions

Acute chest syndrome	Decreased lung function	Hypertension	Renal papillary necrosis
Adenotonsillar disease	Delayed growth/puberty	Hypocalcemia	Reticulocytopenia
Albuminuria	Depression	Hyposthenuria	Reticulocytosis
Amenorrhea	Dizziness	Nephropathy	Retinopathy
Anemia (severe)	Electrolyte imbalance	Osteomyelitis	Retinal hemorrhage
Aplastic crisis	Elevated urinary urobilinogen	Pain, back	Rhabdomyolysis
Arthralgia	Elevated serum transaminases	Pain, chest	Seizure
Avascular necrosis of hip/shoulder	Elevated TCD velocities	Pain, joint	Septicemia
Bacteremia	Fever	Pain, long bone	Silent organ infarction
Bone infarction	Empyema	Pain, severe abdominal	Skin ulcer
Cardiac arrhythmia	Hand-foot syndrome/dactylitis	Pain, sternal or rib	Splenic sequestration
Cardiomegaly	Headache	Priapism	Splenomegaly
Cerebrovascular accident	Hematuria	Proteinuria	Stroke
Cholecystitis	Hemiplegia	Pneumonia	Transient Ischemic Attack (TIA)
Cholelithiasis	Hemolysis	Pulmonary embolism	Transfusion, unanticipated
Cognitive dysfunction	Hepatic sequestration	Pulmonary hypertension	Vaso-occlusive pain
Constipation	Hepatomegaly	Pulmonary infiltrate on chest x-ray	
Cranial nerve palsy	Hospitalization >24 hours	Pyelonephritis	
Death	Hyperbilirubinemia	Renal failure	
Decreased renal function	Hypersplenism	Renal insufficiency	

Table 2. Laboratory Exceptions to the CTCAE List (version 4.0, Guidelines)

Parameter	Grade 2	Grade 3	Grade 4
Hemoglobin (gm/dL)	5.0 – 6.0	4.0 – 4.9	< 4.0
Total WBC ($\times 10^9/L$)	1.0 – 1.999	0.5 – 0.999	< 0.5
ANC ($\times 10^9/L$)	0.5 – 0.999	0.2 – 0.499	< 0.2
Platelets ($\times 10^9/L$)	50 – 79	20 – 49	< 20
Total Bilirubin (mg/dL)	5.0 – 10.0	10.1 – 20.0	> 20.0
AST (IU/L)	150 – 300	301 – 1000	> 1000
ALT (IU/L)	150 - 300	301 – 1000	> 1000
Creatinine (mg/dL)	2Xf baseline serum creatinine and value ≥ 1.0	1.6 – 2.0	> 2.0
ARC ($\times 10^9/L$) and Hb < 7.0 gm/dL	50-80	10-49	< 10

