1.3 Infection Causes Substantial Morbidity and Mortality in African Children with SCA

Infections in children with SCA are a major cause of hospitalization and mortality. The risk of infectious complications in SCA is most evident in low- and middle-income countries (LMICs), where access to care and treatment options are limited. Pneumococcal prophylaxis and pneumococcal vaccination have decreased invasive pneumococcal disease in SCA, but infection remains a common cause of significant illness in African children with SCA. For example, in the NOHARM study of hydroxyurea we recently conducted at the Mulago Hospital Sickle Cell Clinic (MHSCC), children with SCA had an average of 0.7 infections/child/year classified as “severe or invasive” infections (see Appendix I for infections that met this criterion). In addition, two of the three deaths that occurred in the first year of study were attributed to sepsis.

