4.10 Primary Outcome

To assess for the incidence of infections, we will aim to evaluate all illnesses in children during the study period, we will request parents or guardians of children in the ZIPS study to bring their child in to the NSCC or after hours to emergency room at Nalufenya Children's Ward, Jinja Regional Referral Hospital

for any illness. Reimbursement will be provided for transportation, and all medical care will be provided at no cost to the study participant. With this approach in the NOHARM study, children used the MHSCC almost exclusively when they had illness, so we have high confidence that >90% of all illness episodes in this cohort will be taken care of by our study team. We will also record at scheduled visits on month 1, 3, 6, 9 and 12 visits any visits to outside clinics, and illnesses that occurred during those visits. All children will be evaluated for clinical evidence of infection by taking clinical history and exam, and diagnostic work up. Children with a measured axillary temperature of $\geq 37.5^{\circ}\text{C}$ will have blood obtained for a malaria smear and a blood culture for a measured fever of $\geq 38^{\circ}\text{C}$. Children with history of fever or temperature $\geq 37.5^{\circ}\text{C}$ and age-specific tachypnea and cough will have a chest radiograph obtained.

Severe or invasive infections will include: abscesses, bacteremia, cellulitis, diarrhea, dysentery, malaria, meningitis/encephalitis, osteomyelitis, pharyngitis/tonsillitis, pneumonia/acute chest syndrome, sepsis, acute sinusitis. Infections will be defined as outlined in Appendix I (Definitions for Severe and Invasive Infections). We understand that the list is not comprehensive and that clinicians may differ on what constitutes a severe infection, but this list includes the most common infections seen in the NOHARM study that were considered to affect child well-being significantly. Other common infections in this age group (e.g., acute upper respiratory infection (URI), otitis media, conjunctivitis, tinea capitis, tinea corporis) will be recorded, and included (along with the severe and invasive infections) in the category of “clinical infections”. Viral infections with a well-defined clinical picture (e.g., measles, varicella) will be defined by clinical signs and symptoms.

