A codebook with specific definitions for each infection, based on WHO or similar criteria, will be created, and clinicians will have to check off criteria for the infection in order to assign the diagnosis of that infection to the child. Children who have fever with no defined source or clinical syndrome consistent with a specific infectious organisms or clinical syndrome will have a diagnosis of “fever, no defined source”, and will not be included as “clinical infections” because fever could be non-infectious and because a “clinical infection” should conform to a clear clinical diagnosis or have PCR or culture confirmation of infection. Children with culture or PCR confirmed bacterial infections will be a subset of the children with clinical infections, and children with “fever, no source” as their initial diagnosis who are culture or PCR positive for an organism consistent with their clinical syndrome will have the diagnosis corrected to infection with the bacteria or virus confirmed by culture/PCR.

Culture or PCR-confirmed bacterial infections are a secondary objective in this aim. In many severe infections, including pneumonia, sepsis, osteomyelitis, sinusitis, and meningitis, blood cultures are often negative, and they are treated clinically. Other infections that are less severe in children with SCA, such as diarrhea, are typically viral in etiology, yet of clinical significance to these children and are known to be reduced with zinc supplementation. Malaria, which can cause severe disease in children with SCA is also not a bacterial infection. For these reasons, while we acknowledge that severe or invasive infection is a less specific outcome than proven bacterial infection (even with the rigorous definitions we will have in place for severe or invasive infection), we believe it is the right primary outcome for this aim.

For children with pneumonia/ALRI, the multiplex PCR test we use will determine, in addition to infection with *M. pneumoniae* and *C. pneumoniae*, infection with *B. pertussis*, and 17 viruses that commonly cause respiratory infections (see Testing Methods section below). This will provide additional epidemiologic information about viral infections causing febrile or URI syndromes in this population.

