9.0 STATISTICAL ANALYSIS

9.1 Sample Size and Power Calculations

We will assess reduction in incidence of severe or invasive infections, with or without culture or PCR confirmation. Sample size is based on incidence of severe or invasive infections, using a baseline rate of 0.71 infections/child/year, derived from data of children from an earlier clinical trial conducted at MHSCC (the NOHARM study). Power calculations assume an alpha of 0.025 for a one-sided test or 0.05 for a two-sided test. With an incidence of 0.71 severe or invasive infections/year in the placebo group, a sample size of 250 children (with a 10% loss to follow-up) will have 80% power to detect a decrease of $\geq 40\%$ in severe or invasive infection incidence over the 12-month study period. This decrease is smaller than the 47-88% reduction in clinical infection incidence in adolescents and adults in previous studies⁶⁻⁸, so the study sample size should allow us to detect the expected effects of zinc on infection incidence.

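### Appendix I both counts and excludes x-ray-negative pneumonia that meets the sepsis criteria; separately, the 71-episode interim is not at half of the expected events once the 10% loss is applied

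*Combined protocol and SAP*

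**What the plan says.** Section 4.10 lists sepsis and pneumonia/acute chest syndrome as separate severe or invasive infections and refers to Appendix I for definitions. Clinicians assign a diagnosis by checking off the criteria for that infection, from a codebook still to be created.

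In Appendix I:

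- **Pneumonia** needs fever (by history, or at least 37.5°C axillary) "with age-specific tachypnea, cough, and an infiltrate and/or effusion on chest x-ray consistent with pneumonia".
- **The footnote to the pneumonia row** covers children with the clinical signs but no qualifying film: "Children who do not meet radiographic criteria will be given a final diagnosis of “respiratory infection” and not included in primary category". They remain eligible for the secondary endpoint of all clinical infections.
- **Sepsis** needs "2 or more of the following criteria, one of which must be abnormal temperature". The criteria are temperature of at least 38.5°C and age-specific tachycardia, tachypnea or leukopenia. No x-ray, culture or exclusion of another diagnosis is required. The row adds: "Since SIRS in a child with SCA is always suspected to be due to infection, we will use the term sepsis".

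On planning, section 1.3 reports that in the earlier hydroxyurea trial "children with SCA had an average of 0.7 infections/child/year classified as" severe or invasive, and points to Appendix I for the qualifying infections. Section 9.1 uses 0.71 and states that "a sample size of 250 children (with a 10% loss to follow-up) will have 80% power to detect a decrease of" 40% or more. Section 9.2 expects 142 episodes over the two arms and places the single interim analysis at 71, described as half.

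**The concern.** The primary outcome is a count, to be analysed by Poisson or negative binomial regression, and the same count triggers the interim look. If two parts of one appendix classify the same illness differently, two careful blinded analysts can follow the plan and reach different primary counts. If the choice is left until after unblinding, it can be influenced by the result.

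A related gap is that x-ray-positive pneumonia at 38.5°C or above meets two primary definitions. Section 9.1 speaks of infections and section 9.2 of episodes, and neither says that such an illness counts once.

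The interim trigger is a different matter. Sections 9.1 and 9.2 rest on different amounts of follow-up, so the look meant for half of the events would come later than half on the plan's own loss assumption.

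**Working it through.** **1. The two Appendix I texts side by side.** Take an illness with fever, age-specific tachypnea and cough, and a film that does not meet the radiographic criteria.

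| Temperature | Sepsis row | Pneumonia footnote |
|---|---|---|
| By history only, or 37.5–38.4°C | Not met | Not primary |
| 38.5°C or above | Met (temperature + tachypnea) | Not primary |

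Only the second line is in conflict. This takes tachypnea to mean the same in both rows; the wording matches, but the documents give no cut-offs. The footnote makes no exception for an illness that meets another row, and section 4.10 gives no order of precedence. The secondary endpoint of all clinical infections includes the illness under either text.

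**2. The plan's power.** Inputs: placebo rate 0.71 (9.1), rate ratio 0.6 and so zinc rate 0.71 × 0.6 = 0.426 (9.1), 125 per arm (4.6), 10% loss (9.1) and so 112.5 per arm, 12 months, two-sided alpha 0.05. Poisson variance is my assumption.

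- Var(log RR) = (1/0.71 + 1/0.426)/112.5 = 3.756/112.5 = 0.0334; SE = 0.1827
- Power = Φ(0.5108/0.1827 − 1.96) = Φ(0.836) = 79.8%

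The stated 80% is reproduced with the loss applied. At 125 per arm, without loss, the same formula gives 83.8%.

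**3. What the conflict could do to power.** Let s be the disputed illnesses as a share of 0.71. The documents do not give s, so these values are assumptions (112.5 per arm; rate ratio 0.6 for undisputed events).

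| s | In 0.71, excluded in this trial | Not in 0.71, counted here, same zinc effect | Not in 0.71, counted here, no zinc effect on them |
|---|---|---|---|
| 10% | 75.6% | 83.5% | 75.2% |
| 20% | 70.6% | 86.5% | 70.9% |
| 30% | 64.8% | 89.0% | 66.9% |

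At s = 5% the first two columns are 77.8% and 81.7%. If the earlier trial and this one count by the same rule, and zinc acts alike on all events, power stays at 79.8%.

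**4. The interim trigger.**

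- No loss: 125 × (0.71 + 0.426) = 142.0; half is 71.0. This is the plan's figure.
- 10% loss, lost children contribute no time: 112.5 × 1.136 = 127.8; 71/127.8 = 55.6%.
- 10% loss, lost children contribute half a year each (assumption): 118.75 × 1.136 = 134.9; 71/134.9 = 52.6%.

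**The case against.** The strongest reply is that the footnote hangs on the pneumonia row alone. On that view it only says when an illness may be called pneumonia, and every other row applies on its own criteria. Reading it as a general override proves too much: it would also remove an x-ray-negative child with smear-positive malaria or bacteremia, whom Appendix I plainly counts. This stands as a plausible reading and as a limit on any fix. It does not remove the conflict, because the footnote's words exclude the illness from the primary category and not merely from the pneumonia row.

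The group is also narrow: clinical pneumonia, a negative film and 38.5°C or more, within an endpoint that includes malaria, diarrhea, pharyngitis and others. Treatment is double-blind (4.8). Both points stand and limit the consequence. The codebook may settle how an illness meeting two definitions is counted, but it had yet to be created.

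A reader might infer two stronger points.

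- *That 0.71, the 80% power and the 142/71 totals are undermined by the conflict.* The documents do not support this. All the figures reproduce from the stated inputs, 0.71 was counted under whatever rule the earlier trial used, and the link to Appendix I in section 1.3 speaks for a common rule at least as much as for a different one.
- *That section 4.10 contradicts the sepsis row a second time.* It says that fever with no defined source "will not be included as “clinical infections” because fever could be non-infectious", while severe infections are "included (along with the severe and invasive infections) in the category of" clinical infections. But that exclusion is for fever without a source or clinical syndrome, and sepsis is a listed infection with written criteria, which largely answers the point.

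On the interim, 127.8 assumes that lost children contribute no time. That objection is fair, and it is why a range is given.

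**Conclusion.** The conflict holds for x-ray-negative clinical pneumonia at 38.5°C or above, and only there. Its effect on the primary count has no known size or direction: the power figures under assumed shares run from about 65% to 89% and illustrate sensitivity, not the trial's actual power. What remains open is whether this trial will count these illnesses as the earlier trial did.

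The interim point holds in modest form and does not depend on Appendix I. With the loss assumed in 9.1, 71 episodes fall at about 53–56% of the expected total, given the planned rates and zero to half a year of follow-up from each lost child. The plan should be corrected on both points, but neither shows the design to be unsound.

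**What to change.** Before unblinding:

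1. Reconcile the sepsis row and the pneumonia footnote. State whether an illness given a final diagnosis of respiratory infection that also meets the sepsis criteria is a primary event. Limit the rule to the sepsis row, so that x-ray-negative children with, for example, smear-positive malaria or bacteremia still count. Report the other reading as a sensitivity analysis.
2. State that one illness meeting two primary definitions, such as x-ray-positive pneumonia and sepsis, counts as one episode.
3. Confirm that 0.71 was counted under these rules. If not, recount the earlier trial's data, which this team should be able to reach since section 3.0 says it conducted that trial, and re-derive the power and episode totals.
4. Use one loss assumption in sections 9.1 and 9.2, restate the expected total and set the interim at half of it. With the present rates that is 127.8/2 ≈ 64 or 134.9/2 ≈ 67 episodes, depending on the follow-up credited to lost children.

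The cost is a few sentences and at most one recount. The stated power or event total may become slightly less favourable.
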